6.4.4 Safety Analyses

The safety analyses are based on toxicity grades I to V. In general, due to the known neurotoxicity of oxaliplatin a trend to higher toxicity grades is assumed, however, the following limits must not be exceeded:

- not more than 5 percent absolute increase in grade V toxicity in the experimental compared to the control arm
- not more than 5 percent absolute increase in grade V toxicity in the experimental compared to the control arm
- not more than 20 percent absolute increase in grade IV toxicity in the experimental compared to the control arm
- not more than 30 percent absolute increase in grade III toxicity in the experimental compared to the control arm

The initial safety analysis will be conducted six months after study begin, if at least 50 patients in each arm have completed therapy, otherwise at that time point at which at least 50 patients in each arm have completed therapy. Thereafter, safety analyses will be carried out annually and refer to the patient cohort as described in Section 6.3.

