2.2.3 Assessment of Safety

During therapy, patients are monitored weekly for signs of acute toxic effects, with appropriate adjustments in chemotherapy and radiotherapy made as necessary. Assessment of perioperative and 30-day postoperative complications included anastomotic leakage, perineal complications, bleeding, ileus, fistulas, and death.

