6.1. Statistical Endpoints and Hypothesis

Primary endpoint:

To show superiority of the addition of oxaliplatin to neoadjuvant chemoradiotherapy (N-CRT) and to 5-FU-based adjuvant chemotherapy (experimental arm) in comparison to standard N-CRT followed by adjuvant 5-FU monotherapy (control arm) in terms of DFS within three years of follow-up (primary endpoint).

DFS is defined as the time frame between day of randomization and the first day of occurrence of at least one of the following items:

- R2 resection
- local relapse following R0 or R1 resection
- evidence of distant metastasis
- death of the patient

If none of the aforementioned events occur for a randomized patient within the follow-up time, the patient will be censored at the first day at which at least one of the following events occur:

- end or truncation of the study
- study dropout by patient's initiative

The null hypothesis of this study is that there is no statistically significant difference between the experimental and the control arm.

Secondary endpoints were classified as:

- R0 resection rate, circumferential resection margins, quality of TME-surgery
- TNM-classification, number of investigated lymph nodes after quality controlled TME-surgery
- proportion of sphincter-preserving surgical procedures
- tumor regression grading
- cumulative incidence of local relapses and distant metastasis
- overall survival after five years
- acute toxicity of radio- and chemotherapy according to CTC criteria
- late toxicity of radio- and chemotherapy

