6.4.2 Interim Analyses

Since planning of the required sample size harbors uncertainties both for methodological reasons such as assumptions of distributions as well as for the estimation of the effect size, a sequential procedure enabling adaption of the study protocol in terms of sample size makes sense. An interim analysis, which is conducted upon minimal follow-up time for half of the patients, could be carried out at the soonest at 3.5 years after start of study, i.e. when the recruitment phase is completed and the last patients have been treated. Therefore, interim analyses have to be restricted on the confirmatory analysis of secondary endpoints referring to treatment safety. These analyses will be performed annually, starting one year after start of study and will result in study stop if a relevant increase in toxicity in the experimental arm is observed (see Section 6.4.4).

In order to postulate superiority of the experimental arm as early as possible and to be able to offer this treatment to newly diagnosed patients, an interim analysis can be conducted if at least 50% of the recruited patients have completed the minimal follow-up time of two years. In this case, the nominal level of 5% will be divided according to Kim and DeMets 1987 [4]. Thereby, data are based on the proportion of patients with completed follow-up time (DeMets 1985 [5], DeMets 1989 [6]).

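### The toxicity stopping limits are set grade by grade without an or-higher clause, so, counting each patient at worst grade, worsening from grade III to IV can turn a stop into no stop.

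*Protocol*

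**What the plan says.** Section 6.4.4 of the protocol opens with "The safety analyses are based on toxicity grades I to V" and then lists limits on the excess in the experimental arm over the control arm. They are:

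- grade V: "not more than 5 percent absolute increase in grade V toxicity in the experimental compared to the control arm" (this bullet appears twice in identical words)
- grade IV: "not more than 20 percent absolute increase in grade IV toxicity in the experimental compared to the control arm"
- grade III: "not more than 30 percent absolute increase in grade III toxicity in the experimental compared to the control arm"

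The four bullets therefore hold three distinct limits. Section 6.4.2 gives them force: the annual safety analyses "will result in study stop if a relevant increase in toxicity in the experimental arm is observed (see Section 6.4.4"). The first look takes place at six months "if at least 50 patients in each arm have completed therapy", otherwise when that number is reached.

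Two other places bear on what is counted. Section 6.1 lists among the secondary endpoints "acute toxicity of radio- and chemotherapy according to CTC criteria". Section 2.2.3 says: "Assessment of perioperative and 30-day postoperative complications included anastomotic leakage, perineal complications, bleeding, ileus, fistulas, and death". Section 6.4.4 does not say whether a patient is counted once at worst grade, once for every grade experienced, or cumulatively.

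**The concern.** A stopping rule for harm should never become easier to pass because patients are doing worse. Each of these limits is attached to a single grade. If each patient is classified by worst grade, which is a natural way to tabulate toxicity, a patient who moves from grade III to grade IV leaves the grade III count. The grade III excess falls, and the grade IV excess may still lie inside its own limit. Two data sets with the same number of severely affected patients can then lead to opposite decisions, with the more toxic one allowed to continue.

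The primary analysis is not touched. What is at stake is the one numerical rule in the protocol that can stop the trial for toxicity.

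**Working it through.** The protocol gives no error rate or operating characteristic for these limits, so there is no stated figure to reproduce. The check is on the logic of the rule.

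**Inputs from section 6.4.4.** Limits on the excess (Arm A minus Arm B): grade III 30 points, grade IV 20 points, grade V 5 points. First look with at least 50 patients per arm.

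**Assumed inputs.** Arm B worst grade III in 20% and worst grade IV in 3%. Grade V is taken as equal in both arms and left out. The documents give no toxicity rates.

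**Counting at worst grade, each grade on its own**

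| | Arm B | Arm A, case 1 | Arm A, case 2 (15 points worsen III to IV) |
|---|---|---|---|
| Grade III | 20% | 55% | 55 − 15 = 40% |
| Grade IV | 3% | 3% | 3 + 15 = 18% |
| Excess III (limit 30) | | 55 − 20 = +35, breach | 40 − 20 = +20, no breach |
| Excess IV (limit 20) | | 3 − 3 = 0, no breach | 18 − 3 = +15, no breach |

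**Counting cumulatively**

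- III or higher: Arm B 20 + 3 = 23%. Arm A is 55 + 3 = 58% in case 1 and 40 + 18 = 58% in case 2. The excess is 58 − 23 = +35 both times, a breach of 30.
- IV or higher: 0 in case 1 and +15 in case 2.

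The reversal thus occurs under exclusive worst-grade counting and disappears under cumulative counting.

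**How far this depends on the chosen rates.** Start from a grade III excess of D points and no grade IV excess, and let x points of Arm A worsen from III to IV. The excesses become D − x and x. No limit is exceeded when D − x ≤ 30 and x ≤ 20, that is, when D − 30 ≤ x ≤ 20. For D = 35, any shift from 5 to 20 points removes the breach. Such a shift exists for every D above 30 and up to 50. The Arm B rates cancel out of these differences.

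**In patients at the first look (50 per arm).** A limit is exceeded by an excess of 16 patients for grade III (0.30 × 50 = 15, plus 1), 11 for grade IV and 3 for grade V. With an excess of exactly 16 at grade III and none at grade IV, one Arm A patient worsening to grade IV gives 15 and 1, and the breach is gone.

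**Total excess tolerated.** With separate grades, 30 + 20 + 5 = 55 points of excess in worst grade III or higher can be present without a breach. Cumulatively, with the same figures, the maximum is 30 points.

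**The case against.** Several counter-arguments have weight.

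- *The protocol does not prescribe worst-grade counting.* True. The reversal is a property of one reading. Cumulative counting removes it. Counting a patient at every grade experienced also removes it for patients whose grade III event was recorded before the grade IV event. A counting rule might also sit in an analysis plan that is not at hand. But the protocol itself fixes the limits, words each for one grade, and attaches a study stop to them. That wording admits the faulty reading.
- *Worsened patients enter the grade IV count, which has the tighter limit.* Also true, so the signal moves and is not wholly lost. In case 2 the grade IV excess of 15 points is nevertheless inside 20, and no limit is breached.
- *Section 6.4.3 analyses ordinal variables with linear statistics, which would show the shift.* It would, but that test is exploratory and is not one of the limits.
- *The example rates are constructed.* They are, and the 55-point total needs all three limits to be met exactly. The inequality above shows that the reversal does not hang on one set of rates.

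Stronger readings are tempting, and the documents do not support them.

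- A reader might infer that postoperative deaths fall outside the stopping rule. Section 6.4.4 speaks only of toxicity grades and neither includes nor excludes such deaths. The restriction to radio- and chemotherapy comes from an endpoint label in section 6.1. These deaths are not lost to the trial either: they count in disease-free survival and overall survival.
- A reader might infer that the repeated bullet displaced another limit. Nothing shows this, and a repeated limit changes no decision.
- A reader might infer that the rule is weakest where harm is greatest. The limits tighten with grade, from 30 to 20 to 5 points.

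**Conclusion.** The point holds as a conditional one. As worded, the limits permit a reading, worst grade per patient and one grade at a time, under which more severe toxicity can turn a stop into no stop. With the assumed rates, a 15-point shift from grade III to IV changes the excesses from +35 and 0 (breach) to +20 and +15 (no breach), while the excess in grade III or higher stays at +35. At the margin of the first look, one patient is enough. The result rests on that counting rule and on assumed rates. It does not claim that the protocol mandates the rule, that such a shift is likely, or that a grade III-to-IV shift goes unseen.

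The duplicated grade V bullet and the status of 30-day postoperative deaths are matters for clarification, not faults in the rule.

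**What to change.** Apply the limits in section 6.4.4 cumulatively to each patient's worst grade: grade III or higher, grade IV or higher, and grade V. The data are already collected, so the work is a change of wording.

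It is still a change of substance. If the printed figures are kept, the boundary becomes stricter: the permitted excess in grade III or higher falls from 55 to 30 points, and the limits will be reached sooner. The sponsor should therefore confirm the figures on the cumulative scale.

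Two clarifications should go in at the same time:

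- Reconcile the repeated grade V bullet, either by deleting it or by stating what was meant.
- State whether the 30-day postoperative deaths collected under section 2.2.3 count as grade V, and show them by arm at each safety look.

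The second choice has a cost to weigh. If all deaths counted whatever their cause, an excess of 3 at 50 per arm would breach the limit. With equal true mortality in both arms (assumed), the binomial chance of such a false breach is 0.9% at 1% mortality, 3.6% at 2% and 6.7% at 3%.
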